8.3.2 Direct access to source data and documents

The investigator /institution will allow site program-related monitoring, audits, IRB / IEC review and regulatory inspections. Direct access must be provided to the CRF and all source documents/data, including progress notes, copies of laboratory and medical test results, which must be available at all times for review by the CRA, auditor and regulatory inspector (e.g. FDA). They may review all CRFs and informed consents. The accuracy of the data will be verified by direct comparison with the source documents described in section [8.3.1](#). The sponsor will also monitor compliance with the protocol and GCP.

8.3.3 Storage period of records

Program site(s):

The program site(s) must retain the source and essential documents (including ISF) according to contract or the local requirements valid at the time of the end of the program (whatever is longer).

Sponsor:

The sponsor must retain the essential documents according to the sponsor's SOPs.

8.4 EXPEDITED REPORTING OF ADVERSE EVENTS

BI is responsible to fulfil their legal and regulatory reporting obligation in accordance with regulatory requirements.

8.5 STATEMENT OF CONFIDENTIALITY AND PATIENT PRIVACY

Individual patient data obtained as a result of this program is considered confidential and disclosure to third parties is prohibited with the exceptions noted in section [8.7](#).

Data protection and data security measures are implemented for the collection, storage and processing of patient data in accordance with the principles 6 and 12 of the WHO GCP handbook.

Personalised treatment data may be given to the patient's personal physician or to other appropriate medical personnel responsible for the patient's welfare. Data generated at the site as a result of the program need to be available for inspection on request by the participating physicians, the sponsor's representatives, by the IRB / IEC and the regulatory authorities.

8.6 PROGRAM MILESTONES

The **start of the program** is defined as the date when the first patient in the whole program signs informed consent.

The **end of the program** is defined as the date when the last patient completes the follow up period after the last [REDACTED] of spesolimab in the whole program ("Last Patient Completed").

The "**Last Patient Last Treatment**" (LPLT) date is defined as the date on which the last patient in the whole program is administered the last dose of the treatment (as scheduled per protocol or prematurely). Individual investigators will be notified of SUSARs occurring with the treatment medication until 30 days after LPLT at their site.

Early termination of the program is defined as the premature termination of the program due to any reason before the end of the program as specified in this protocol.

Temporary halt of the program is defined as any unplanned interruption of the program by the sponsor with the intention to resume it.

Suspension of the program is defined as an interruption of the program based on a Health Authority request.

8.7 ADMINISTRATIVE STRUCTURE OF THE PROGRAM

The program is sponsored by Boehringer Ingelheim (BI).

A Coordinating Investigator is responsible to coordinate investigators at the different sites participating in this program. Tasks and responsibilities are defined in a contract.

Relevant documentation on the participating (Principal) Investigators (e.g. their curricula vitae) will be filed in the ISF.

The investigators will have access to the BI web portal Clinergize to access documents provided by the sponsor.

BI has appointed a Clinical Trial Leader (CTL), responsible for coordinating all required activities, in order to:

- manage the program in accordance with applicable regulations and internal SOPs,
- direct the clinical program team in the preparation, conduct, and reporting of the program,
- ensure appropriate training and information of Clinical Trial Managers (CTM), Clinical Research Associates (CRAs), and investigators of participating countries.

The organisation of the program in the participating countries will be performed by the respective local or regional BI-organisation (Operating Unit, OPU) in accordance with applicable regulations and BI SOPs, or by a Contract Research Organisation (CRO) with which the responsibilities and tasks will have been agreed and a written contract filed before initiation of the clinical program. On-site monitoring will be performed by BI or a contract research organization appointed by BI.

Data Management and Statistical Evaluation will be done by BI according to BI SOPs or by a CRO with which the responsibilities and tasks will have been agreed and a written contract filed before initiation of the clinical program.

Tasks and functions assigned in order to organise, manage, and evaluate the program are defined according to BI SOPs. A list of responsible persons and relevant local information can be found in the ISF.

An IRT vendor will be used in this program. The physician will receive all necessary instructions to access the IRT system from the Sponsor. Detailed IRT functions and procedures will be documented in the IRT Manual available in the ISF.

10. APPENDICES

10.1 APPENDIX 1: CLINICAL CRITERIA FOR DIAGNOSING ANAPHYLAXIS

Anaphylaxis is highly likely when any one of the following 3 criteria are fulfilled:

1. Acute onset of an illness (minutes to several hours) with involvement of the skin, mucosal tissue, or both (e.g., generalised hives, pruritus or flushing, swollen lips /tongue / uvula)

AND AT LEAST ONE OF THE FOLLOWING

- a. Respiratory compromise (e.g., dyspnea, wheeze-bronchospasm, stridor, reduced PEF, hypoxemia)
 - b. Reduced BP or associated symptoms of end-organ dysfunction (e.g., hypotonia [collapse], syncope, incontinence)
2. Two or more of the following that occur rapidly after exposure to a likely allergen for that patient (minutes to several hours):
 - a. Involvement of the skin-mucosal tissue (e.g., generalised hives, itch-flush, swollen lips / tongue / uvula)
 - b. Respiratory compromise (e.g., dyspnoea, wheeze-bronchospasm, stridor, reduced PEF, hypoxemia)
 - c. Reduced BP or associated symptoms (e.g., hypotonia [collapse], syncope, incontinence)
 - d. Persistent gastrointestinal symptoms (e.g., crampy abdominal pain, vomiting)
3. Reduced BP after exposure to known allergen for that patient (minutes to several hours):
 - a. Infants and children: low systolic BP (age specific) or greater than 30% decrease in systolic BP*
 - b. Adults: systolic BP of less than 90 mm Hg or greater than 30% decrease from that person's baseline

PEF, Peak expiratory flow; BP, blood pressure.

*Low systolic blood pressure for children is defined as less than 70 mm Hg from 1 month to 1 year, less than (70 mm Hg +[2 x age]) from 1 to 10 years, and less than 90 mm Hg from 11 to 17 years.

Reference: [R11-4890](#)

11. DESCRIPTION OF PROTOCOL AMENDMENT(S)

Version 1.0 update to version 2.0

Section number	Description of change
Table 1.4:1 Risks associated with spesolimab administration	Peripheral neuropathy added. Update made according to updated IB.
3.2.3 Exclusion criteria	New exclusion criteria added: 7. Presence of acute myelinating neuropathy. Update made according to updated IB.
3.2.4.1 Discontinuation of trial medication and assessment	New stopping rule added for myelinating neuropathy. Update made according to updated IB.
5.2.4.1.4. Adverse evenst of special interest	Event suspected or diagnosed as peripheral neuropathy added. Update made according to updated IB.
3.1 Overall program design and plan	New flow chart added

2. LIST OF ABBREVIATIONS

See Medicine Glossary:

<http://glossary>

Term	Definition / description
AE	Adverse event
AESI	Adverse event of special interest
BI	Boehringer Ingelheim
BIcMQ	Boehringer Ingelheim customized MedDRA Query
BMI	Body mass index
CRF	Case report form
CTP	Clinical trial protocol
CTR	Clinical trial report
ECG	Electrocardiogram
eCRF	Electronic case report form
EMA	European Medicines Agency
EOS	End of study
EOT	End of treatment
ES	Enrolled set
GPP	Generalized pustular psoriasis
GPPGA	Generalized Pustular Psoriasis Physician Global Assessment
i.v.	intravenous
ICH	International council for harmonisation of technical requirements for pharmaceuticals for human use
iPD	important protocol deviation
IQR	Interquartile range
MedDRA	Medical dictionary for regulatory activities
OR	Original results
PT	Preferred Term
Q1	1 st quartile
Q3	3 rd quartile
REP	Residual effect period
SAE	Serious adverse event
SAP	Statistical analysis plan
SAS	Statistical analysis software

Term	Definition / description
	dose
SD	Standard deviation
SMQ	Standardised MedDRA query
SOC	System organ class
TEAE	Treatment emergent adverse event
TS	Treated set
TSAP	Trial statistical analysis plan
UDAEC	User-defined adverse event categories
WHO-DD	World health organisation – drug dictionary

3. INTRODUCTION

As per ICH E9 ([1](#)), the purpose of this document is to provide a more technical and detailed elaboration of the principal features of the analysis described in the protocol, and to include detailed procedures for executing the statistical analysis of the primary and secondary variables and other data.

This TSAP assumes familiarity with the Clinical Trial Protocol (CTP), including Protocol Amendments. In particular, the TSAP is based on the planned analysis specification as written in CTP Section 7 XXXXXXXXXX. Therefore, TSAP readers may consult the CTP for more background information on the study, e.g., on study objectives, study design and population, treatments, definition of measurements and variables, planning of sample size, randomization.

SAS® Version 9.4 or higher will be used for all analyses.

Note that this TSAP applies to trial 1368-0073 (including Revised Protocol # 2 [c36703857-02]), 1368-0077 (including Revised Protocol # 2 [c39436286-01]), 1368-0109 under the Expanded Access Program.

4. CHANGES IN THE PLANNED ANALYSIS OF THE STUDY

Not applicable.

5. ENDPOINTS(S)

5.1 PRIMARY ENDPOINT(S)

The primary endpoint is defined in CTP Section 2.1.2.

5.2 SECONDARY ENDPOINT(S)

5.2.1 Key secondary endpoint(s)

Not applicable.

5.2.2 Secondary endpoint(s)

Secondary endpoints are listed in CTP Section 2.1.3.

6. GENERAL ANALYSIS DEFINITIONS

6.1 TREATMENT(S)

The following treatment option is planned in the study:

- [REDACTED] Dose [REDACTED] : spesolimab [REDACTED]
- [REDACTED] Dose [REDACTED] : spesolimab [REDACTED] at Day [REDACTED] and Day [REDACTED]

The study phases are defined relative to spesolimab at Day 1 as below:

Table 6.1: 1 Flow chart of analysis phases of the study for each flare

Study analysis phase	Description	Start (included)	End (included)
Screening phase	Screening	Earliest of i) Date of informed consent, ii) first screening procedure	Date/time of start of [REDACTED] minus 1 minute
Treatment phase (including REP if applicable)	On-treatment period	Date/time of start of [REDACTED] (Day 1)	Earliest of: i) Date of end of last [REDACTED] + 112 days at 23:59, ii) Date of end of study visit, iii) Date/time of start of screening for next flare
Follow-up phase ¹	Off-treatment period	Date of end of [REDACTED] of last study treatment + 113 days at 0:00 a.m.	Latest of: i) Date of EOS visit; ii) Last contact date on End of Study page at 23:59

Dates are defined individually per patient. REP represents the residual effect period. An analysis phase will not extend beyond the start date of the following phase.¹ The follow-up phase only exists if the last contact date is after the date of [REDACTED] of last study drug + 112 days.

Note that in the trial, a patient experiencing a new GPP flare may re-enter the study within/after the [REDACTED]-week follow-up period, starting from screening again. For details, refer to section 3.1 in CTP. Therefore, a patient may have more than one screening/flare treatment/follow-up period.

Data across all flare treatment periods will be pooled and handled per patient, with "Overall Speso [REDACTED]" to label the treatment group.

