7.8.1 Adverse Events

AEs will be coded with the most recent version of MedDRA. Patients will be analyzed according to the actual treatment received.

The analysis of AEs will be based on the concept of treatment emergent AEs. This means that all AEs will be assigned to the screening phase, treatment phase or follow-up phase as defined in [Section 6.1](#). Since only the start date of an AE is collected (without start time), any AE occurrence on the same day as spesolimab at Day 1 will be assigned to the on-treatment period.

The primary endpoint of occurrence of treatment emergent adverse events (TEAE), will be analysed as the exposure-adjusted adverse event incidence rates in all flare treatment period based on TS by using per patient analysis for TEAE.

Per patient analysis for TEAE

- 1) The exposure adjusted incidence rate (per 100 patient years) of a selected treatment emergent adverse event is defined as the number of patients experiencing the adverse event per treatment group during time at risk divided by the total time of patients at risk in that treatment group to contribute the event to the analysis multiplied by 100 (per 100 patient years).

Time at risk [patient years] = (date of onset of AE – first treatment start date within that treatment period + 1) / 365.25

For all flare treatment period on a patient level, each flare treatment period is combined with the previous flare treatment period as defined in [Section 6.1](#).

- 2) If, for a patient, the selected treatment emergent adverse event didn't occur during the above defined treatment period (per [Section 6.1](#)) then the time at risk will be censored at the earliest of date of death, last contact date per EoS page, or the end of the above defined treatment period.

For each selected treatment emergent AE, the exposure adjusted incidence rate will be calculated as:

Incidence rate [1/100 Patient years (pt-yrs)] = 100 * number of patients with TEAE / Total TEAE-specific time at risk [patient years].

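### SAP Table 6.1: 1 leaves recorded adverse events between an early end-of-study visit and day 112 in no analysis phase, so they drop out of the treatment-emergent tables

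*SAP*

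**What the plan says.** **Protocol.** Section 7.1.1 assigns all adverse events with onset from start of treatment to the end of the residual effect period, 16 weeks after the last dose, to the on-treatment period. It makes no exception for an early EoS visit. The primary endpoint (AEs) and both secondary endpoints (SAEs, AESIs) in Section 2.1 are all treatment-emergent.

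Footnote 3 of the flow chart in Section 3.1 asks first that a patient who stops early complete all visits, and failing that attend Visit 6 at a set number of weeks after the last administration. For patients who refuse to return, it plans an early EoS visit at discontinuation and then a safety contact by phone. Section 3.2.4.1 puts a final contact at 16 weeks after the last drug intake and asks for new AEs to be recorded where possible.

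**SAP.** Table 6.1: 1 ends the on-treatment period at the earliest of last administration plus "112 days at 23:59, ii) Date of end of study visit", or the start of screening for the next flare. The follow-up phase begins at the end "of last study treatment + 113 days at 0:00 a.m". It runs to the later of the EoS visit and the "Last contact date on End of Study page at 23:59". Two notes apply: "An analysis phase will not extend beyond the start date of the following phase", and "The follow-up phase only exists if the last contact date is after the date of" last drug administration plus 112 days.

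Section 7.8.1 then states that "all AEs will be assigned to the screening phase, treatment phase or follow-up phase". For a patient without the event, "then the time at risk will be censored at the earliest of date of death, last contact date per EoS page". The close of the on-treatment period is the third limit in that list. Section 4, headed "CHANGES IN THE PLANNED ANALYSIS OF THE STUDY", is marked as not applicable.

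**The concern.** The 112/113 pairing shows that adjacent phases were intended. The EoS criterion breaks this. If the EoS visit comes before day 112, the days from that visit to day 112 are after the on-treatment period and before follow-up. The protocol arranges a call that can pick up events from those days, but the SAP has no phase to put them in.

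For these patients all three safety endpoints are therefore computed over a shorter window than protocol 7.1.1 defines. The table also conflicts with the SAP's own statement that all AEs go to one of three phases, and the departure is not declared. The programme is small, descriptive and about safety, so even one omitted SAE or AESI would be visible in the tables.

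**Working it through.** **1. The window.** 16 weeks × 7 = 112 days, so the SAP's first criterion reproduces the protocol window. The difference comes from the other criteria.

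**2. Applying the table.** Count days after the last administration. Let E be the EoS visit, C the last contact and S the start of re-screening, if any.

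- On-treatment ends at min(112, E, S).
- Follow-up starts at 113, and exists only if C > 112.
- With no re-screening and E < 112, an onset on day d with E < d ≤ 112 is in neither phase. It is not in screening either, which ends before the first administration.
- Unassigned days = 112 − E.

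| EoS visit, day E | Unassigned days | Share of 112 |
|---|---|---|
| 8 | 104 | 93% |
| 28 | 84 | 75% |
| 56 | 56 | 50% |
| 105 | 7 | 6% |
| 112 or later | 0 | 0% |

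The early days are illustrative. Day 105 is the early edge of the ±7-day window if Visit 6 is planned at week 16, which is an assumption because the week is redacted.

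**3. Do the table notes close the gap?** The first note prevents overlap between phases; it does not extend a phase up to the next one. A last contact on day 112 or day 119 changes nothing, because follow-up never starts before day 113.

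**4. What depends on it.** Assignment goes by onset date. An event first mentioned at the call but with onset on or before the EoS visit stays on-treatment. Only later onsets are lost.

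**5. Direction.** Removing events from the numerator while keeping the patient in the denominator can only lower counts and percentages. For the exposure-adjusted rate, let D be patients with an event and T the time at risk, and let the cut remove d and t. The rate becomes (D − d)/(T − t), which exceeds D/T whenever d/t < D/T. Either direction is possible.

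Phase II figures in protocol 1.2.3 show why a rise is plausible. The spesolimab arm had 35 patients (19/0.543), with SAEs in 14.3% = 5/35 by week 1 and 25.7% = 9/35 by week 12. Assuming a constant hazard within each interval:

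- Week 0–1: −ln(30/35) = 0.154 per week.
- Weeks 1–12: −ln(26/30)/11 = 0.0130 per week.

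The early hazard is about 12 times the later one, so the cut would remove mostly low-rate time.

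As an illustration only, carry the later hazard to week 16 and let 5–20% of patients have an EoS visit at week 1 at unchanged risk. The percentage with an SAE falls from 29.5% to 28.7–26.4%, while the rate rises from 122 to 125–134 per 100 patient-years. The 5–20% has no source in the documents, and the model assumes that the call finds every SAE. It shows direction, not size.

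**6. Checking the repair.** Let on-treatment end at min(112, max(E, C), S). With E = 28 and C = 112 it ends at day 112; with E = 7 and C = 119 it also ends at day 112. No recorded onset up to day 112 and up to last contact is then unassigned, unless S comes first.

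**The case against.** **Few patients are affected.** This stands. Footnote 3 makes the early EoS visit a last resort. For completers seen early in the Visit 6 window, no later contact is planned, so few events would be recorded in the at most 7 days concerned.

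**Internal standards may settle it.** SAP 7.8.1 refers to two sponsor documents on AE summarisation and incomplete AE dates, which are not available here. They could hold a rule. But the SAP itself defines the phases, and its text has none for this case.

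**The analysis is descriptive and the rate adjusts for exposure.** Events and time at risk are indeed cut together, so the rate is not necessarily too low. The counts and percentages planned alongside it have no such protection.

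Three stronger readings are tempting but not supported:

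- *Deaths, cancers and drug-related SAEs of consent-withdrawn patients are lost through this table.* Protocol 5.2.4.2.1 ends a patient's programme at withdrawal of participation. It says that cancers and drug-related SAEs and AESIs learned of after the end of programme are not entered in the CRF. On that wording they are missing because of the data-capture rule, whatever the table says, and no special counting rule for these patients is warranted.
- *The events disappear altogether.* Only the treatment-emergent tables are affected. Listings and expedited reporting may still show them.
- *Repairing the EoS criterion puts every onset up to day 112 on-treatment.* It does not. Onsets after re-screening for a new flare still go to the new screening phase under the third criterion.

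**Conclusion.** The gap is certain on the wording of SAP Table 6.1: 1, and it contradicts both protocol 7.1.1 and SAP 7.8.1 without being declared. It affects patients who discontinue prematurely, have an EoS visit before day 112 and then give safety information by phone, insofar as those events are recorded in the CRF. Their number cannot be estimated from the documents and is probably small. For each such patient the loss can be most of the window; through the Visit 6 window it is at most 7 days if that visit is planned at week 16.

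Patients with treatment-emergent AEs, SAEs or AESIs can only be undercounted. The direction for the exposure-adjusted rate, the planned primary measure, is open. This should be fixed before the analysis, mainly because the remedy is so small.

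**What to change.** In SAP Table 6.1: 1, replace the second criterion for the end of the on-treatment period with: the later of the EoS visit and the last contact date on the End of Study page. Keep the 112-day cap and the re-screening criterion. Apart from onsets after re-screening, every recorded onset up to day 112 and up to last contact is then on-treatment, and time at risk under SAP 7.8.1 ends at the same date. The existing note still prevents overlap.

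The cost is one criterion in one table. The SAP already uses the last contact date in the follow-up row and in the censoring rule. The repair relies on that date including the safety call, so this should be confirmed.

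If the sponsor prefers the present cut, one line in SAP Section 4 should declare it as a departure from protocol 7.1.1.

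Separately, protocol 3.2.4.1 and 5.2.4.2.1 should be reconciled on what the 16-week contact records: any new AE, or only the restricted list, and whether it enters the CRF.

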7.1.1 Safety analyses

In general, safety analyses will be descriptive in nature and will be based on BI standards. No hypothesis testing is planned.

Adverse events will be coded using the Medical Dictionary for Drug Regulatory Activities (MedDRA). Standard BI summary tables and listings will be produced. Statistical analysis and reporting of adverse events will concentrate on treatment-emergent adverse events, i.e. all adverse events occurring between start of treatment and end of the REP, a period of 16 weeks after the last dose of program medication. Adverse events that start before first drug intake and deteriorate under treatment will also be considered as 'treatment-emergent'. All adverse events with an onset between start of treatment and end of the REP, a period of 16 weeks after the last dose of program medication, will be assigned to the on-treatment period for evaluation.

All treated patients will be included in the safety analysis.

Frequency, severity, and causal relationship of adverse events will be tabulated by system organ class and preferred term. after coding according to the current version of the Medical Dictionary for Drug Regulatory Activities (MedDRA) at database lock.

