7.7 EXTENT OF EXPOSURE

Treatment exposure is defined as the total dose of randomized spesolimab [mg] received per patient. In general, the total dose of spesolimab [mg] received per [REDACTED] is calculated as the

total [REDACTED] volume [mL], as documented on the eCRF, times the strength prepared in the [REDACTED]

Strength in [REDACTED]
[REDACTED]

The duration of the [REDACTED] trial treatment [minutes] at each visit will be calculated as the end of the [REDACTED] date/time minus the start of the [REDACTED] date/time.

The number of doses will be calculated, which is based upon the number of visits at which doses of study drug were administered.

Time at risk will be assessed in months per definition in [Section 7.8.1](#), where the end date will be the end of each flare treatment period in [Table 6.1: 1](#).

The duration of [REDACTED], the number of doses, time at risk and the total dose [mg] will be summarised by descriptive statistics (N, mean, SD, minimum, Q1, median, Q3, maximum), using per patient analysis for all flare treatment period.

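### SAP Table 6.1: 1 ends the on-treatment period at re-screening for a new flare, which shortens the protocol's 16-week adverse-event window without declaring a change

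*SAP*

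**What the plan says.** Protocol 7.1.1 defines the window used for evaluation: "All adverse events with an onset between start of treatment and end of the REP, a period of 16 weeks after the last dose" belong to the on-treatment period. It makes no exception for re-entry. Protocol 3.1 and 6.1.3 and SAP 6.1 all allow a patient with a new flare to re-enter during follow-up.

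SAP Table 6.1: 1 ends the on-treatment period at the earliest of three dates:

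- limb i: 112 days after the end of the last administration;
- limb ii: the end-of-study visit;
- limb iii: "iii) Date/time of start of screening for next flare".

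The note under the table makes the same cut: "An analysis phase will not extend beyond the start date of the following phase".

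The safety analysis is built on these phases. SAP 7.8.1 states: "This means that all AEs will be assigned to the screening phase, treatment phase or follow-up phase". It adds that "any AE occurrence on the same day as spesolimab at Day 1 will be assigned to the on-treatment period". Where a patient has several flares, "each flare treatment period is combined with the previous flare treatment period as defined in" Section 6.1. For time at risk, SAP 7.7 points to the same table: "where the end date will be the end of each flare treatment period in" Table 6.1: 1.

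SAP Section 4, which is the place for departures from the protocol's planned analysis, reports none.

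**The concern.** Limb i reproduces the protocol window and limb iii does not. A patient re-screened for a new flare within 16 weeks of the last dose is still inside the protocol's residual effect period, but the SAP moves that patient into a new screening phase. An AE that starts between re-screening and the new dose then drops out of the treatment-emergent tables.

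The endpoints are occurrence of treatment-emergent AEs, serious AEs (SAEs) and AEs of special interest (AESIs). Compared with the protocol window, limb iii can only lower the number of patients with a given event or leave it unchanged. The exposure-adjusted rate can move either way, because time at risk may shrink as well.

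The excluded days are not a neutral sample. The patient is flaring at that time, and Protocol 1.1 links flares to systemic symptoms and sepsis.

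**Working it through.** **Inputs.** The residual effect period is 16 weeks (Protocol 7.1.1). Limb i is 112 days and limb iii is the start of re-screening (SAP Table 6.1: 1). AEs on the new Day 1 are on-treatment (SAP 7.8.1). Screening and dosing may fall on the same day (Protocol 3.1, flow chart footnote 1).

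**Check of limb i.** 16 × 7 = 112 days, so limb i matches the protocol.

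**Days lost through limb iii.** Let s be the re-screening day, counted from the last dose, and g the days from re-screening to the new dose. The re-screening day is the included end of the old period, so I count it as on-treatment. If it is not, add one day wherever g is at least 1. Limb ii is assumed not to apply first.

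Re-dosed: days lost = max(0, min(g - 1, 112 - s)). This equals max(g - 1, 0) unless day 112 comes first.

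| g | s = 28, 56 or 84 | s = 105 |
|---|---|---|
| 0 | 0 | 0 |
| 1 | 0 | 0 |
| 3 | 2 | 2 |
| 7 | 6 | 6 |
| 14 | 13 | 7 |

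Re-screening on or after day 112 loses nothing.

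Not re-dosed: two readings are possible.

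- The new screening phase runs on. Days lost = 112 - s, which is 84 (75%), 56 (50%) or 28 (25%) for s = 28, 56 or 84.
- Phases exist only around a dose, as the lead-in to the table suggests ("The study phases are defined relative to spesolimab at Day 1 as below"). With no new Day 1 there is no new screening phase, limb i applies, and the loss is 0.

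**Effect on a rate (illustration only).** Assume 20 patients with one dose per flare, two patients with an AESI on Day 20, and one other patient re-screened on Day 57 (56 days after the dose). A full on-treatment period is Day 1 to Day 113, or 113 days. Rate = 100 × patients with the event / (days at risk / 365.25), the SAP 7.8.1 formula.

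Case A, not re-dosed:

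- No further AESI, protocol window: 18×113 + 2×20 = 2074 days; 2 patients; 35.2 per 100 patient-years.
- No further AESI, SAP with screening running on: 17×113 + 57 + 40 = 2018 days; 2 patients; 36.2. Under limb i, 35.2.
- AESI on Day 70, protocol window: 17×113 + 70 + 40 = 2031 days; 3 patients; 54.0.
- AESI on Day 70, SAP with screening running on: 2018 days; 2 patients; 36.2. Under limb i, 3 patients and 54.0.

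Case B, re-dosed on Day 64, so the second period is Day 64 to Day 176 (113 days) and Days 58 to 63 are lost (6 days):

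- No further AESI, protocol window: 17×113 + 176 + 40 = 2137 days; 2 patients; 34.2.
- No further AESI, SAP: 17×113 + 57 + 113 + 40 = 2131 days; 2 patients; 34.3. If gap days count as at risk, 2137 days and 34.2.
- AESI on Day 60, protocol window: 17×113 + 60 + 40 = 2021 days; 3 patients; 54.2.
- AESI on Day 60, SAP: 2 patients; 34.3, or 34.2 if gap days count.

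**Any-AE count.** Inclusion criterion 2 (Protocol 3.2.2) requires the re-entering patient to be in a flare already, and Protocol 5.2.4.1.1 has worsening of the underlying disease recorded as an AE. The new flare should therefore be an AE with onset on or before re-screening, inside the SAP's on-treatment period. The patient is already counted, and time at risk for the any-AE rate stopped at or before that onset.

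**The case against.** **Limb iii has a protocol basis.** Protocol 6.1.3 ends the current follow-up and restarts the patient at screening. This explains where limb iii may come from. It does not redefine the residual effect period in 7.1.1, and a re-screened patient is still within 16 weeks of the last dose.

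**The flare periods are combined.** They are combined as Section 6.1 defines them, so the gap stays out. The sentence also leaves open whether gap days count as time at risk.

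**Pre-dose AEs that worsen count as treatment-emergent.** Protocol 7.1.1 says so, but this recovers only gap events that worsen after a new dose. It does not recover an event that resolves first, or one in a patient who is not re-dosed.

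**The headline endpoint is barely touched.** This stands, for the reason in the last step of the working, provided investigators record the flare as an AE. In the earlier placebo-controlled trial in Protocol 1.2.3, 91.4% of patients randomised to spesolimab had an AE by week 12, so an any-AE count has little room to move. SAEs were less common there, at 25.7%.

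**The large contrasts are assumed.** This also stands. The drop from about 54 to about 34 to 36 comes from placing one patient's only AESI in the gap. Without it, the rates differ by at most 1.0 per 100 patient-years.

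**Gaps should be short.** Protocol 6.1.1 lets dosing proceed at once when the patient is eligible, and re-entry within follow-up needs agreement with the sponsor. Both limit the exposure, and neither removes the conflict.

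**Conclusion.** The two documents define different on-treatment windows for a patient re-screened within 112 days of the last dose, and the SAP does not declare the difference. The loss is max(g-1, 0) full days for a patient re-dosed g days later, capped at day 112. For a patient not re-dosed it is either 0 or the rest of the 112 days. The consequence falls on SAEs, AESIs and individual system organ class and preferred term rows, where patient counts can only fall or stay the same. The analysis is descriptive, no test is involved, and the number of re-entries is not stated. The total effect therefore cannot be fixed and is probably small.

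A reader might infer three stronger things that the documents do not support:

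- That the primary any-AE result is materially understated. The new flare should already count as an AE on or before re-screening.
- That 28 to 84 days are certainly lost for patients not re-dosed. This depends on a reading that the SAP leaves open.
- That AEs go uncollected. Protocol 5.2.4.2.1 requires collection until 16 weeks after the last dose, and for a patient not re-dosed that date does not move. The fault is in classification, not in data capture.

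**What to change.** 1. In SAP Table 6.1: 1, replace limb iii with the start of the first administration for the next flare.
2. Add a precedence rule. For a re-entering patient, the on-treatment period prevails over the new screening phase until the earlier of the last administration + 112 days and the new first administration. Amend the Screening row and the table note to match. Without this, the new screening phase would still start at consent or first procedure and overlap the extended on-treatment period.
3. In SAP 7.7 and 7.8.1, use the same days for time at risk as for counting AEs, and say so for the combined flare periods.
4. Check the wording against the other two protocols that SAP Section 3 names, which were not available here.

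If the sponsor prefers to keep limb iii, SAP Section 4 should declare it as a departure from protocol 7.1.1, and Section 6.1 should state the phase rule for a patient re-screened but not re-dosed.

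With items 1 and 2 in place, limb iii removes no days from the protocol window. The cost is a few lines of SAP text and a small programming change. No new data are needed, given the AE collection that the protocol already requires.
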